- 2) Basal systemic inflammation levels: systemic inflammation (interleukin [IL]-6; C-reactive protein [CRP]) is reduced following both moderate (Thompson et al., 2010; Stewart et al., 2007; Fedewa et al., 2017) and vigorous (Munk et al., 2011; Stewart et al., 2007) intensity exercise training. Inflammatory cells and cytokines support cell growth, survival and spread (Grivennikov, Greten and Karin, 2010), and medication with anti-inflammatory agents decreases incidence and recurrence of a number of cancers (Rayburn, Ezell and Zhang, 2009). It is hypothesised that the anti-inflammatory effects of regular exercise may also ameliorate neoplastic activity.
- 3) Metabolic factors and hormone levels: insulin and insulin-like growth factor [IGF]-1 are reduced, and IGF binding protein [IGFBP]-3 is increased with moderate-vigorous intensity aerobic exercise (Francisco Meneses-Echavez et al., 2016). This results in a lower bioavailability of metabolic factors and hormones which are associated with growth and survival of MM cells (Bieghs et al., 2016), and may lead to reduced neoplastic growth.
- 4) Body composition: visceral adipose tissue is significantly reduced following moderate (Slentz et al., 2005) and vigorous (Irving et al., 2008) intensity aerobic exercise. Body composition change may mediate the mechanistic link between an exercise-induced reduction in systemic inflammation and neoplastic activity, as visceral adipose tissue secretes high quantities of inflammatory cytokines in obese individuals (Fontana et al., 2007) and exercise-induced reductions in inflammation are greater when a reduction in body fat is also measured (Fedewa, Hathaway and Ward-Ritacco, 2017). The resulting reduction in chronic, systemic inflammation as a result of reduced cytokine production by smaller visceral fat stores, may reduce tumour growth, survival and spread (as explained above).

Progressive resistance exercise is incorporated into the supervised exercise sessions in this study to; (i) to support safe progression through the incremental aerobic exercise programme, (ii) to add variety to the exercise classes to maintain participant enjoyment and motivation to attend, (iii) for diverse outcomes for older adults, e.g. reduce falls risk (Buchner et al., 1997).

A home-based session has been included to increase exercise frequency without the additional burden of visits on participant's time and research feasibility. Home-based sessions are also being evaluated for potential use in a future, larger randomised-controlled trial. Walking exercise has been selected as this is an intervention that is accessible to the majority of people with MGUS and SMM.

Supervised exercise sessions

Supervised exercise sessions will be performed in the physiotherapy gym at the Royal United Hospital Bath. Each session lasts approximately 1 hour, and equipment needed for all exercises is available in the physiotherapy gym, including resistance bands and treadmills. A brief screening, including blood pressure measurement and review of health status, will take place before each supervised session to determine safety to exercise (unsafe if: blood pressure >200/120 mmHg (Ats and Accp, 2003) or participant reports new symptoms).

Exercise sessions will be offered at various times throughout the day so the programme is accessible to as many participants as possible, including those with diverse/busy routines (e.g. working / retired). Each exercise class has a maximum capacity of five participants per session. There will be drop-in sessions available for participants who have not been able to attend their scheduled exercise sessions.

Aerobic component

Participants will perform a warm up on the treadmill at a comfortable walking speed and 0% incline ('unloaded walking') for a minimum of 5 minutes. Aerobic training will then commence for 30 minutes. Participants will perform

three sets of 10-minute walking intervals (Table 2). For each interval, the gradient is increased during the 'work phase' to achieve a target HR (8 minutes, 40-80% VO_{2MAX}) followed by 'unloaded walking' (2 minutes). Target HR will be prescribed and monitored using HR data measured during CPET; participants will be given a HR zone that corresponds to the target percentage of VO_{2MAX}. An RPE guide (Borg 6-20 scale) will be used for people who present with a blunted HR response during CPET (e.g. medicated with beta blockers) as their HR response will be too small to differentiate zones that span a 10% change in VO_{2MAX}.

The Polar A370 will be worn with a chest strap HR monitor (Polar H10) during every supervised exercise session to prescribe intensity and record the session. The HR, RPE, speed and gradient will be recorded for each interval.

[figure not shown]
Table 2.	Table 2. Aerobic exercise prescription								
Trial	Number of	Work duration	ork duration Work phase Work phase Rest duration Total duration						
week	intervals	(minutes)	intensity (% VO _{2MAX})	intensity (RPE)	(minutes)	(minutes)			
1-2	3	8	40-50	12-13	2	30			
3-6	3	8	50-60	13-14	2	30			
7-10	3	8	60-70	14-15	2	30			
11-16	3	8	70-80	15-16	2	30			

The primary outcome of the trial is to assess the safety and feasibility of exercise in people with MGUS and SMM. We anticipate this prescription to be safe, as older adults with heart failure can safely perform interval training up to 95% HR_{MAX} (Wisloff et al., 2007), and people with symptomatic MM – a much more severe form of disease than MGUS and SMM – can safely exercise up to 60% heart rate reserve (Groeneveldt et al., 2013). The programme has been designed to allow gradual adaptation whilst steadily progressing to vigorous intensity over 16 weeks to maximise anti-tumour benefits by stimulating adrenaline-dependent immune cell redistribution (Pedersen et al., 2016). Treadmill walking has been selected because: (i) whole-body exercise elicits a robust array of physiological benefits compared to aerobic exercise of confined muscle groups (e.g. cycling or arm-crank); (ii) weight-bearing exercise improves bone strength (McMillan et al., 2017); and (iii) it is more accessible and can be more readily replicated in the real world, as compared to other exercise modalities.

Resistance component

A whole-body resistance training programme will be performed using elastic resistance band exercises. Elastic resistance bands provide a cheap and simple method of applying resistance. The programme progresses every four weeks targeting increase in muscular strength (Table 3).

Participants will perform two sets of 12-6 repetition maximum (RM) of six large muscle group exercises (reverse fly, chest fly, core twist, squat, calf raise, abduction) in line with resistance training guidance for people with a cancer diagnosis (Galvao et al., 2007). During a familiarisation session, the researcher will identify the colour of resistance band and grip rating that gives 12 RM for each exercise (e.g. level 1-5; diagram below) (Smith et al., 2017). This will be reassessed prior to each structured progression. To ensure continued progression, participants will be instructed to work past the prescribed RM and if they exceed the repetition target then additional resistance will be added prior to the next set/session by increasing grip rating or band colour (Cormie et al., 2013).

During familiarisation, the researcher will demonstrate each exercise and give feedback on a return demonstration performed by the participant. During subsequent sessions, circuit cards will be positioned around the physiotherapy gym to prompt correct technique and the researcher will be on-hand to provide assistance if needed. Participants will be asked to record the number of repetitions they perform, RPE, band colour and grip rating for each set in their session record card.

Version 3.1 19/DEC/18

Table 3. Resistance exercise prescription							
Trial week	Number of sets	Number of exercises	RM prescription				
1-2	2	6	15				
3-6	2	6	12				
7-10	2	6	10				
11-16	2	6	8				

Home-based exercise

Participants will be asked to complete one 40-minute walk each week at a moderate intensity (RPE 12-14) and daily balance and flexibility exercises (performed on days without a supervised session) which are detailed in the Home Exercise Pack. This increases the weekly aerobic exercise volume to 75-150 minutes at a moderate-vigorous intensity, and increases the frequency of balance and flexibility exercises, in line with WHO guidelines for physical activity in older adults.

Behaviour change

Psychological sources of behaviour are important to consider when introducing a novel behaviour, i.e. an exercise programme, in order to optimise uptake, adherence, compliance and retention. Additionally, developing positive psychological processes in participants should increase the likelihood of continuing exercise after the trial ends for maintenance of any benefits attained. This reflects clinical practice in other exercise-based therapies delivered by the NHS (e.g. cardiac rehabilitation involves ~12 weeks of outpatient exercise classes [phase 3], after which patients transition to independent, ongoing conditioning in the community [phase 4]). In light of this, behaviour change techniques from a standardised taxonomy (Michie et al., 2011) have been included in the trial design (Table 4).

Table 4. Behaviour change con	siderations
Behaviour change technique	Implementation in present trial
Informational support	 Participants will be given detailed information about the exercise programme in the recruitment material, and will be encouraged to ask questions to ensure they understand the programme and the trial. At the end of the trial, the researcher will provide participants with information on local exercise referral schemes.
Information on consequences of behaviour	 The recruitment material describes the positive effects of exercise for health, explaining the rationale behind each component of the programme, which will be reinforced by the researcher during face-to-face interactions. Participants will be given a feedback report highlighting the health benefits attained during the exercise programme.
Feedback on performance	• Participants will be given regular feedback on how well they are meeting the progression targets set out in the exercise programme.
Self-monitoring	 Participants will be given a fitness tracker (Polar A370) to record habitual physical activity and home-based exercise, which will give feedback on their progress.
Instruction on how to perform behaviour	• The researcher will teach the participants how to perform the different exercises outlined in the exercise programme.
Social support	 Group exercise sessions will create a social environment for related peers, with the aim to keep classes at consistent times for each participant to allow relationships to be formed within the group. The researcher will facilitate grouped home-based exercises by identifying walking routes/meeting points for local participants.

Action planning	٠	The exercise programme has a highly prescriptive action plan for 16 weeks.

Benefits of participating

Participants will be provided with bespoke feedback on their test results after completing the trial period. This will include physical activity levels, dietary composition, blood pressure, body composition, cardiorespiratory fitness and physical capacity, with reference to population norms and recommended guidelines – and highlighting any changes that occur between baseline and follow-up measures. We will not be providing feedback on data collected from blood samples because most of the measurements are preliminary research parameters and are not diagnostic; routine blood test results will continue as normal and participants will have access to these results as per routine.

Abnormal results from the CPET will be flagged up with the haematologist, who may advise referral to another healthcare professional (e.g. general practitioner or cardiologist) which will be done by letter or email. In this case, 'abnormal' is defined as the presence of a criteria for exercise contraindication or early test termination, as defined in CPET guidelines (Ats and Accp, 2003).

Participants will receive 32 supervised exercise sessions for free, which would typically cost upwards of £320 privately (i.e., £10 per session).

Participants will be given an information sheet upon completing the exercise programme with recommendations on staying active upon completion of this study. This will include a home-exercise programme and resistance bands provided free of charge, and information on local exercise referral schemes.

Participants will be receive a payment of £100.00 in cash at the end of the trial. This amount covers costs associated with travel, calculated based on the number and average distance to travel for trial visits, and parking costs.

Risks of participating

The trial has been designed to reduce risks and burdens as much as possible, with the further aim of reducing potential risks and burdens further by strict adherence to best practice.

The exercise components of the trial (maximal treadmill exercise test and exercise programme sessions) carry a risk of injury and acute complications.

- The acute risks of exercise will be minimised by performing thorough screening at trial entry via medical note review by the haematologist, PARQ, blood pressure checks, and resting and exercise ECG.
- We will also assess risk before each exercise training session by asking participants if they have had any symptoms of health change since their last session, and measuring their blood pressure prior to exercise.
- Exercise training will be personalised to each individual based on their fitness level and ability so as to promote a safe exercise training programme.
- All exercise sessions will be undertaken at the Cancer Research Suite at Bath Royal United Hospital. The Cancer Research Suite is located within the physiotherapy department, and is thus in close proximity to nurses and other care specialists with first aid training. Adjacent to the Cancer Research Suite is an emergency trolley bed, and an emergency telephone for contacting accident and emergency or other care services.

Another consideration is that participants will undergo a body composition assessment by DEXA which uses a very low dose radiation. Participants will be advised that this scan allows the most accurate (i.e. 'gold-standard') measurement of their body composition (e.g. fat, bone mineral density) and it is safe, with each scan eliciting a dose of radiation equivalent to a very short airplane flight (e.g. from London to Paris).

Taking a blood sample via venepuncture brings risks including pain, bleeding, bruising, embolism and infection. These risks are controlled by adherence to best practice. People with MGUS and SMM will be very familiar with the sensations associated with a blood test as this is the primary way their disease is monitored routinely.

Wearing activity monitors for prolonged periods may, in some cases, result in some minor skin irritation, but this will be minimal and good practice minimises this risk. Participants will be provided with verbal and written information on how to use the activity monitors to minimise this risk.

An important consideration for the research team when designing this study was the amount of time each participant will have to commit to the trial, which includes: 1 hour of screening and consenting, up to 5 hours of measurement visits and, finally, 32 exercise sessions (32 separate one hour visits). The screening visit has been planned to coincide with usual clinic hours at the haematology outpatients, so that people will be accustomed to the timing of this session, the familiarity of the physical environment and the practicalities of attending (e.g. parking, navigation of hospital). Trial measurement visits will be scheduled at a time of day according to the participant's availability. The exercise sessions will be run throughout the day and evenings to allow participants to choose the most suitable time for them to attend. These time considerations were made so that people who want to enrol, but are limited in terms of time availability can participate (e.g. if they have a job).

Statistics and data analysis

Sample size

The aim is to recruit 20 participants. Assuming a recruitment rate of three to four people per month and 15% drop out, we estimate the target can be reached within a suitable time-frame so the findings can be submitted for a PhD thesis (12-15 months).

There is limited information available to enable a formal sample size calculation. This pilot trial will provide preliminary data to determine that a future RCT has promise and is not futile, and to perform a sample size calculation.

Statistical analysis plan

Primary outcome measures do not lend themselves to statistical analysis. Feasibility will be reported as proportions in terms of uptake, adherence, compliance and retention. Safety will be reported as the incidence and severity of adverse events.

Secondary data will be tested for normality (e.g. Shapiro-Wilk) and in the event that some data are not normally distributed, the data will be log transformed. Descriptive statistics will be presented, and longitudinal differences and interaction effects will be identified using repeated-measures T-tests. These data will be used to inform sample size calculations in a future RCT. Incomplete data and missing values will be managed using an intention-to-treat approach with multiple imputation.

The PhD project may utilise correlation analysis to establish whether any change in disease activity is associated to a number of mechanistic markers, and stepwise multiple regression will identify the extent to which a change in the mechanistic markers predict change in disease activity. Subgroup analysis may be performed, e.g. split to high vs. low responders or by presence of mediating variable(s) for further analysis.

Monitoring, audit and inspection

The University of Bath, as Sponsor, will monitor and conduct random audits on a selection of studies in its clinical research portfolio. Monitoring and auditing will be conducted in accordance with the Department of Health Research Governance Framework for Health & Social Care (April, 2005), and in accordance with the Sponsor's monitoring and audit policies and procedures.

Patient safety will be monitored on an ongoing basis by the research and healthcare team. A formal data monitoring committee will not be convened as this is a small single-centre pilot study. Instead, the lead researcher (PhD Student, [name]) will present an update on safety at quarterly trial management group meetings, together with the haematologist ([name]), the CI and primary PhD supervisor ([name]), secondary PhD supervisor ([name]) and patient representative(s).

Ethical and regulatory considerations

Research Ethics Committee (REC) review

Before the start of the trial, approval will be sought from an NHS REC for the trial protocol, informed consent forms, participant information sheet and recruitment letter. Substantial amendments will require review by the NHS REC will not be implemented until the NHS REC grants favourable opinion.

Public and patient involvement

A group of people diagnosed with MGUS and SMM were invited to the University of Bath on the evening of Wednesday 23rd November 2017 to discuss the proposed trial design with the research team. Discussions were held on the following topics, with feedback on each point was incorporated into the trial protocol and other trial documents:

- Proposed recruitment strategies, including invitation letters and follow-up invitation phone calls from the haematology department.
- Wording of trial documents, including the participant information sheet and consent forms.
- Practicalities of participant involvement in the trial, including: total time commitment, time of day preferences for people who are retired and people who are in full-time work, travel to the different research sites (University of Bath and Royal United Hospital), and financial reimbursement for travel.
- All research measurements being taken in this trial, including blood sampling, DEXA (body composition) scans, and the exercise fitness test.
- Design of the exercise programme, including discussions about acceptability of treadmill walking exercise, preferences for class-based exercise sessions rather than private one-to-one exercise sessions.
- Use of fitness trackers (i.e. Polar A370) to monitor participant physical activity levels throughout the trial, which including discussion about patient desire to wear such technology as this is a motivating factor for them to lead a healthier lifestyle.

People with MGUS and SMM will also be involved in the analysis of results via the trial management group, and dissemination of findings through Myeloma UK – for which [name] (haematologist) Chairs meetings of the Myeloma UK South West group.

Regulatory compliance

Procedures for DEXA scanning are compliant with Ionising Radiation (Medical Exposure) Regulations and have been reviewed by a Medical Physics and Clinical Radiation Expert.

Protocol compliance

Prospective, planned deviations to the protocol are not allowed under the UK regulations on research trials. Accidental deviations can happen at any time and should be documented and reported to the CI. Frequently recurring deviations can be classified as a serious breach. Deviations are not anticipated as the research team is relatively small, and each member has been closely involved in the writing of this protocol.

Competing interests

There are no competing interests that will influence design, conduct or reporting of this trial.

Indemnity

The Sponsor (University of Bath) insurance will cover the legal liability for harm to participants arising from the design, management and conducting of this research.

Amendments

Substantial amendments to the documents submitted in the original REC application will be submitted using a valid notice of amendment to REC and to the trial sponsor. Non-substantial amendments will be made throughout the trial as needed. The CI will be responsible for determining whether an amendment is substantial. Substantial amendments will be highlighted in a new version of the document.

Data management and confidentiality

The University of Bath will act as the Data Controller for data generated by this trial.

Identifying data (name, date of birth, contact details and next of kin details) will be kept by the Royal United Hospitals Bath NHS Foundation Trust. This data will be stored in a password-protected Excel spreadsheet on a desktop computer stored in a locked room. This data will be deleted following the final study contact during the eight-month follow up. Signed consent forms will be stored in a locked cupboard and kept for 10 years to evidence the consent process.

Deidentified study data, coded with a unique study ID assigned to each participant, will be kept by the University of Bath. This data will be stored on the University of Bath X Drive which is backed up daily by the Library. The study-specific folder can only be accessed by the research team. Hard copies of trial data will be stored in a locked cupboard at the University of Bath. Study data will be kept for 10 years in line with the University of Bath research data policy (see: http://www.bath.ac.uk/research/data/policy/index.html).

Post-trial care

Participants will be given an information sheet upon completing the exercise programme with recommendations on staying active. This will include a home-exercise programme plus resistance bands, and information on local exercise referral schemes.

The researcher will telephone participants eight months following visit 4 – representing a full year since they entered the study. They will ask questions about current physical activity habits and identify participants who need additional information on how to lead an active lifestyle. Further signposting will be provided as a duty of care.

Access to the final trial dataset

All protocol contributors named in this document will have access to the final trial dataset. Requests for access by other researchers within the Department for Health at the University of Bath will be approved by the trial management group.

Dissemination policy

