Exercise may also be an effective way to improve global health in MGUS and SMM. Indeed, structured exercise programmes has been found to improve a wide range of health outcomes in people with haematological cancers (e.g. MM, Hodgkin lymphoma, non-Hodgkin lymphoma). People with haematological cancers who perform structured exercise show improvements in quality of life, fatigue, strength (Groeneveldt et al., 2013; Persoon et al., 2017; Furzer et al., 2016; Joske et al., 2013) and cardiorespiratory fitness (Persoon et al., 2017; Furzer et al., 2016; Joske et al., 2013). High adherence was reported in these trials (85%: (Joske et al., 2013); 87%: (Groeneveldt et al., 2013); 91%: Version 3.1 19/DEC/18

(Furzer et al., 2016); 86%: (Persoon et al., 2017)) with no adverse events related to trial participation. Given that exercise is safe in these most advanced diseases, exercise is likely safe in MGUS and SMM, but this is yet to be evaluated. Accordingly, this study aims to confirm the feasibility and safety of exercise, as well as preliminarily explore the effects of exercise on disease activity, fitness and wellbeing outcomes, with a view to evaluating these outcome measures in a future, larger randomised-controlled trial.

In addition to establishing the benefits of exercise in MGUS and SMM, this study provides a unique methodological model to investigate the effects of exercise on neoplastic activity in humans. Given the relatively non-invasive and inexpensive measures of disease activity used in MGUS and SMM (e.g. M-protein, free light chains) which enable real-time monitoring of tumour flux, and the absence of confounding therapies (e.g. chemotherapy) that are typical of other cancer diagnoses, MGUS and SMM provide a unique model to prospectively assess the short-term effects of exercise on tumour activity *in vivo*, and in doing so conduct mechanistic investigations to discover how regular exercise averts tumour growth in humans. A number of anti-tumour mechanisms of exercise have been proposed, including immune function, inflammation and metabolic hormones (McTiernan, 2008), which will be explored as secondary outcome measures in our study herein.

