In summary, the present pilot study aims to assess the feasibility and safety of an exercise programme in MGUS and SMM, and to provide preliminary data on disease activity, fitness and wellbeing outcomes for sample size calculations in a larger randomised controlled trial (RCT). Additionally, as part of this pilot study, a PhD project will investigate the potential mechanisms involved in possible changes in disease activity. Pilot data will allow a future larger randomised controlled trial to be designed optimally and to be adequately powered to assess the effect of exercise on disease activity, mechanisms and global fitness and wellbeing outcomes in MGUS and SMM. The unique clinical model proposed herein is anticipated to improve our wider understanding of how physical activity is linked to reduced cancer risk.

Aims and outcomes

The present trial will investigate the feasibility and safety of a 16-week progressive, walking-based exercise programme for MGUS and SMM.

Primary objectives and outcomes, measured throughout the trial period:

- Uptake (proportion of people approached who attend screening, proportion of people who attend screening that are deemed eligible)
- Adherence (proportion of supervised and home-based exercise sessions prescribed that are actually completed)
- Compliance (prescribed vs. actual aerobic exercise completed per supervised/home-based session)
- Retention (the proportion of participants who complete baselines measures that also complete follow-up measures)
- Safety (incidence and severity of adverse events)

Secondary objectives and outcomes, measured pre- and post-trial period:

- Disease activity of MGUS and SMM (M-protein, serum free light chains, beta-2 microglobulin)
- Physical fitness (VO_{2MAX}, balance, flexibility, strength)
- Free-living physical activity (e.g. duration, intensity, frequency, energy expenditure) and sedentary time (also measured during 8-month follow-up)
- Body composition (height, weight, waist and hip circumference, fat mass, lean mass, sagittal abdominal diameter)
- Wellbeing indices (frailty, fatigue, sleep, quality of life)
- CRAB indices (e.g. calcium; renal function [creatinine, estimated glomerular filtration rate; eGFR]; anaemia [full blood count, haemoglobin]; bone health [bone mineral density, bone mineral content, bone turnover biomarkers])
- Resting blood pressure and heart rate

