Participants will complete a Session Record Card in each supervised session. Home-exercise will be monitored using a Home Exercise Diary which will be reviewed each week. Participants will also be provided with a fitness tracker (Polar A370 wrist-worn device) for the duration of the trial period to record all training sessions. Data from the tracker will be downloaded by the researcher once a week, and the tracker will be returned after Visit 4.

The primary outcome of feasibility refers to the overall viability of the exercise intervention (e.g. how well can we recruit, can we keep participants engaged, are participants able to achieve the exercise intensities required) and the safety (e.g. do adverse events occur and are they unexpected and related to the trial treatment):

Uptake: Proportion of people approached who attend screening (recruitment rate) and the proportion of people who attend screening that are deemed eligible (screen-pass rate). Demographic characteristics will be compared across those who a recruited and those who decline to participate.

Adherence: Number of supervised and home-exercise sessions completed measured using a Session Record Card, Home Exercise Diary and Polar A370.

Compliance: Prescribed vs. actual aerobic exercise completed in each supervised session will be measured using the Polar A370 and chest strap HR monitor. Compliance to home-based aerobic exercise will be measured using the Polar A370.

Retention: Proportion of participants who complete baselines measures (i.e. Visit 1 and 2) that also complete followup measures (i.e. Visit 3 and 4).

Safety: Incidence and severity of adverse events (Table 1). [Recording and reporting of SAEs will follow University of Bath policy – The chief investigator (CI) should report any SAE to the sponsor within 24 hours. A written SAE report (health research authority [HRA] form) should be made by the lead researcher and sent to the CI who will assess the seriousness, causality and expectedness. Where the SAE is related and unexpected, the CI will notify the research ethics committee (REC) within 15 days of receiving the report. AEs and SAEs will be discussed by the trial management group.]

Table 1. Definitions of a	Table 1. Definitions of adverse events						
Term	Definition						
Adverse Event (AE)	Any untoward medical occurrence in a participant to whom an intervention has been administered, including occurrences which are not necessarily caused by or related to that product.						

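### Relatedness and expectedness are part of the safety question but are assessed only for serious events, so that part cannot be answered for non-serious adverse events

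*Protocol*

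**What the plan says.** The safety question appears in the Protocol under *Trial period measurements*, in the paragraph introducing the primary outcome. Safety is illustrated there as "do adverse events occur and are they unexpected and related to the trial treatment". The words stand in a parenthesis that opens with e.g.

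The outcome itself is given three times, each time as incidence and severity:

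- *Aims and outcomes*: "Safety (incidence and severity of adverse events".
- *Trial period measurements*: "Safety: Incidence and severity of adverse events (Table 1".
- *Statistical analysis plan* section of the protocol: "Safety will be reported as the incidence and severity of adverse events".

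Table 1 makes the AE count all-cause by definition, "including occurrences which are not necessarily caused by or related to that product".

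Attribution appears once, in the bracketed text on SAE reporting under *Trial period measurements*. The written SAE report is "sent to the CI who will assess the seriousness, causality and expectedness". The use made of that judgement follows: "Where the SAE is related and unexpected, the CI will notify the research ethics committee (REC) within 15 days". For AEs in general, the same text adds only that the trial management group will discuss them together with SAEs.

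**The concern.** Safety stands beside feasibility as a primary objective, and the *Trial design* section describes a single arm. Without a control group, a count of all AEs cannot by itself separate harm from the programme from background illness. The main tool left is a judgement, event by event, on whether the programme was responsible.

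The protocol provides that judgement for serious events only. Yet *Risks of participating* names injury and acute complications as the risks of the exercise components, and many events of that kind (a strain, joint pain, a dizzy spell) would be non-serious. Participants are also asked about symptoms before each supervised session, which means 2 × 16 = 32 times over the programme. That will tend to bring in complaints that have nothing to do with exercise.

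At stake is what the final report can say. It could state how many AEs occurred, but for non-serious events not how many were thought to be caused by the walking and resistance programme, nor how many were unexpected. The trial management group, which advises the sponsor on continuing, modifying or stopping the trial, would likewise have no recorded attribution for those events.

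**Working it through.** The protocol gives no figure for safety to reproduce, so the check sets the question against what is recorded and what is reported.

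| Part of the question | Non-serious AEs | SAEs |
|---|---|---|
| Do events occur? | Yes: incidence is an outcome | Yes: incidence is an outcome |
| Are they related? | No assessor, criteria or record stated | Assessed by the chief investigator; not named in the outcome or analysis text |
| Are they unexpected? | No assessor, criteria or record stated | Assessed by the chief investigator; not named in the outcome or analysis text |

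1. *Does any other section extend the assessment to non-serious AEs?* No. *Monitoring, audit and inspection* describes a quarterly safety update to the trial management group, and *Roles and responsibilities of the trial management group* says that the group monitors safety data. Neither states that relatedness or expectedness is judged or recorded.
2. *Can the single arm supply attribution indirectly?* No. There is no concurrent rate to compare with.
3. *Could a separate statistical analysis plan repair this?* Only in part. It could tabulate SAEs by the chief investigator's judgement. It could not tabulate judgements on non-serious AEs that were never collected.

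**Illustration on assumed rates.** The protocol gives neither a background AE rate nor an injury rate, so both are assumptions here. Let a proportion p of the 20 participants have at least one unrelated AE, and let the programme independently injure 2 of the 20. The expected number with any AE is then 20p without the injuries and 20p + 2(1 − p) with them.

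| Assumed p | No injuries: 20p | Two injured: 20p + 2(1 − p) | Related cases |
|---|---|---|---|
| 0.40 | 8 | 8 + 1.2 = 9.2 | 0 to 2 |
| 0.50 | 10 | 10 + 1.0 = 11 | 0 to 2 |
| 0.70 | 14 | 14 + 0.6 = 14.6 | 0 to 2 |

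On these assumptions the all-cause count rises by 0.6 to 1.2 participants, while the related count rises by 2. This shows the mechanism only. It applies if reporting comes down to a count of participants with any AE, which the protocol does not say.

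**The case against.** The best case for the plan runs as follows. The wording on relatedness is an example, not the definition, and the definitions agree with each other. All-cause incidence is a legitimate and conservative outcome. The bracketed text concerns expedited reporting and does not claim to list everything recorded about AEs. The trial management group includes the chief investigator and the haematologist and discusses all AEs. With 20 participants, each event can be described individually. The pilot sets no safety test or threshold, so no decision rule changes.

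Much of this stands. The definitions do not conflict, and all-cause incidence is a sound outcome to keep. Two things remain. The example is the protocol's most specific statement of what the safety outcome should show. And a discussion that is not recorded leaves nothing to report.

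A reader might infer more than the text supports:

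- *That the safety question cannot be answered at all.* It can in part: occurrence is counted, and SAE causality is assessed.
- *That the results cannot be set against earlier trials.* *Background and summary* does describe those trials as "with no adverse events related to trial participation", but no comparison of AE rates with them is planned, and how they attributed events cannot be seen from the protocol.
- *That severity is undefined.* Table 1 separates serious from non-serious events without a severity grade, but a grading scale is a detail often left to other trial documents and is not part of this point.

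**Conclusion.** The point holds in a limited form. As written, the trial would hold no recorded judgement of relatedness or expectedness for any non-serious AE. For SAEs the judgements exist, but the outcome and analysis text does not call for reporting them. The gap lies in data collection, so it needs a protocol change.

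Its size cannot be derived from the protocol. That non-serious events will form most of the harm from such a programme is an assumption, though a reasonable one. The numerical illustration rests wholly on assumed rates and does not carry the conclusion.

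A reader might also infer that the primary safety outcome should become related AEs. The protocol gives no good ground for that. The trial is unblinded, and the chief investigator who assesses SAEs is also the lead researcher's primary PhD supervisor. A headline based on investigator attribution could understate harm.

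**What to change.** 1. Under *Trial period measurements*, extend the assessment of causality and expectedness from SAEs to every AE. Name the chief investigator or the haematologist as assessor and state the criteria. Record the judgement on the AE log at the time of the event, along with its setting: supervised session, home session or exercise test.
2. In *Aims and outcomes*, *Trial period measurements* and the *Statistical analysis plan* section, state that incidence and severity will be reported both for all causes and by relatedness and expectedness.
3. Keep all-cause incidence as the outcome, with the attributed counts beside it.

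The cost is a few extra columns on the AE log and a few minutes per event, from people who already discuss AEs. The drawback is that relatedness judgements are subjective and made unblinded, which is why the all-cause counts must stay in the report.
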